15.4 Adverse Event Reporting

All adverse events will be recorded in the case report form. The investigator is responsible for the appropriate medical management of all adverse events. Any serious and unexpected adverse event will be reported to the medical monitor immediately by telephone or fax and follow-up the call with a written report within five days. Full details of the event, any sequelae and an assessment of the relationship to the study medical device will be provided in the report. Any serious and unexpected adverse events and all deaths will also be reported to the EC or IRB within ten days and a copy of this report will be sent to the medical monitor. Exalenz Bioscience will notify all investigators of serious or unexpected adverse events when this information is of global importance to subject safety and welfare. Exalenz Bioscience or its designee will report all adverse events to the FDA, EC and other competent authorities.

A written report is required for all patients who die within 30 days after the end of their participation in the study. This report must document the events surrounding the patient's death and the cause of death. Attach a copy or summary of autopsy findings, if performed.

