9.2 Safety Objective

All adverse events, serious adverse events (SAE) and suspected unexpected serious adverse reactions (SUSAR) will be reported according to local regulations. The actual reporting is discussed in section 15 below. No breath-test related adverse events are expected.

For more information please refer to the Investigator Brochure.

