10.6 Safety Termination of Subjects or Study

1. Withdrawal of patients from the study if they have a CTCAE Grade 3 or higher regardless of whether the event is attributed to the drug unless it is caused by an accident that could not reasonably be attributable to the drug (CTCAE: Common Terminology Criteria for Adverse Events Version 4.0).
2. Discontinuance of study, if ≥ 2 patients administered Octanoate / Methacetin develop the same CTCAE Grade 3 event or 1 patient develops a CTCAE Grade 4 or higher event due to one of the breath tests.

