Life threatening is defined as an event in which the patient is at risk of death at the time of the event. It does not refer to an event that hypothetically might have cause death if it was more severe. Disability is defined as a substantial disruption of a person's ability to conduct normal life functions. An unexpected adverse event is one that has not been previously observed, or one that is of a specificity or severity not consistent with the current investigator brochure.

When an adverse event occurs, record the following information and assessments in the adverse event section of the CRF:

- The signs, symptoms, or diagnosis of the event
- The date and time of onset of the event using the 24 hour clock where midnight is 00:00 and noon is 12:00
- The adverse event severity using the criteria outlined below
- The relationship of the event to the study medical device as outlined below
- Describe any action taken regarding study medical device disposition
- List any required therapy, medication, treatment, or diagnostic procedure.

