15.3 Adverse Event Severity

- Mild Adverse Events

A mild adverse event is one that the symptoms are barely noticeable to the patient. It does not influence performance, require drug treatment or prevent the patient from carrying on with normal life activities.

- Moderate Adverse Events

Exalenz Bioscience Ltd.	Last update on: May1, 2016
Study Title: Clinical Study of the BreathID [®] System to train the algorithm for the ¹³ C-Octanoate Breath Test with or without the ¹³ C-Methacetin Breath Test (OBT and MBT respectively) for correlation with histological findings of Non-Alcoholic Fatty Liver Disease (NAFLD)	Protocol No.: NASH-EX-1114
	Version: 1f
Document N^o: CSD00080	Page 46 of 61

A moderate adverse event is one that the symptoms make the patient uncomfortable and causes some impairment to normal life activities. Treatment for symptom(s) may be required.

- Severe Adverse Events

A severe adverse event is one that the symptoms cause severe discomforts to the patient and severely limits the patient's normal daily activities. Treatment for symptom(s) is given.

Note: Serious and severe are not synonymous. A serious adverse event must fulfill the requirements listed in the definition above.

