15.5 Study-Specific Exceptions

Disease complications or death as a result of disease progression is expected and it is not necessary to report them as SUSARs, but they should be reported in the follow-up section of the case report form (CRF).

Exalenz Bioscience Ltd.	Last update on: May1, 2016
Study Title: Clinical Study of the BreathID [®] System to train the algorithm for the ¹³ C-Octanoate Breath Test with or without the ¹³ C-Methacetin Breath Test (OBT and MBT respectively) for correlation with histological findings of Non-Alcoholic Fatty Liver Disease (NAFLD)	Protocol No.: NASH-EX-1114
	Version: 1f
Document N^o: CSD00080	Page 47 of 61

Furthermore, the following situations and non-fatal toxicities that fulfill the definition of an AE are excluded from expedited notification on an AE form, but should be reported in the follow-up section of the CRF form:

- Elevation of bilirubin
- Elevation liver enzymes
- Nausea, vomiting , diarrhea

Lastly, the following elective procedures should be excluded from expedited notification on an SAE form and should be reported in the follow-up section of the CRF form:

- Central and arterial line insertion, intubation and ventilation, tracheostomy
- Liver transplantation

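### The 10.6 stopping rule counts events by CTCAE grade, but 15.4 requires prompt notice only of serious and unexpected events, so a non-serious Grade 3 event counts toward stopping with no reporting deadline

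*Combined protocol and SAP*

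**What the plan says.** Section 10.6 ends the study if at least two dosed patients develop "the same CTCAE Grade 3 event or 1 patient develops a CTCAE Grade 4 or higher event due to one of the breath tests". It also withdraws any patient with a Grade 3 or higher event, whatever the cause, accidents aside. Section 10.7 asks that withdrawals be documented but names no recipient and no time limit.

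For how events are reported, section 9.2 points forward: "The actual reporting is discussed in section 15 below". Section 15.4 then sets these timed duties:

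- "Any serious and unexpected adverse event will be reported to the medical monitor immediately by telephone or fax", with a written report within five days.
- Serious and unexpected events and all deaths go to the EC or IRB within ten days, copied to the medical monitor.
- A written report is required for deaths within 30 days after participation ends.

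Every other event is recorded in the CRF, with no entry deadline. Section 15.3 warns: "Serious and severe are not synonymous".

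Section 15.1 tells sites to "record the following information and assessments in the adverse event section of the CRF". The severity item on that list is "The adverse event severity using the criteria outlined below", which means the mild, moderate and severe scale of 15.3. CTCAE grade is not on the list.

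Section 15.5 adds an exemption. For raised bilirubin, raised liver enzymes, nausea, vomiting and diarrhea, "non-fatal toxicities that fulfill the definition of an AE are excluded from expedited notification on an AE form". These go to the follow-up section of the CRF. No upper grade is set.

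**The concern.** A stopping rule that counts patients across sites works only if someone central learns of each qualifying event in time. No single site can see that a second patient elsewhere has had the same Grade 3 event. Here the rule is driven by CTCAE grade, while the prompt-reporting duty is driven by seriousness and unexpectedness. An event can satisfy the first without the second. One patient at each of two sites could then complete the trigger while all sites go on dosing, with no one in breach of the protocol.

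Two features make it harder to recognise a trigger from the data. The top level of the listed scale, severe, does not distinguish Grade 3, where two patients are needed, from Grade 4, where one is enough. And events on the 15.5 list are sent to a different part of the CRF from the one that holds severity and relationship.

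**Working it through.** No figure in the plan needs reproducing. The check sets the events that count under 10.6 beside the timed routes in section 15 (numbering as in the body of the protocol).

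| Event due to a breath test | Counts under 10.6 | Timed notice in 15.4 |
|---|---|---|
| Grade 3, not serious | Yes, two patients | None; CRF only |
| Grade 4, not serious | Yes, one patient | None; CRF only |
| Grade 3 or 4, serious and unexpected | Yes | Immediate call |
| Grade 3 or 4, serious but expected | Yes | No immediate call |
| Fatal | Yes | Ten days, with copy to the medical monitor; immediate if unexpected |

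The fourth row is nearly empty in practice. Section 9.2 expects no breath-test related events, so a serious one would normally be unexpected and belong to the third row. Most Grade 4 events would probably meet a seriousness criterion in 15.1, such as being life-threatening, so the second row is small. What remains is mainly the first row.

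The other provisions do not supply a deadline. Section 10.7 sets none for documenting a withdrawal. The 48-hour safety call in 12.5 has no stated onward time limit. Section 17.1 estimates monitoring at a minimum of every 3 months per site or every 10 subjects.

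**Illustration of delay.** The inputs are 200 patients (11.5) and 6 to 12 months of enrolment (10.8). Even accrual is assumed.

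- Rate: 200/12 = 16.7 to 200/6 = 33.3 patients per month.
- One day: 200/365 = 0.55 to 200/182.5 = 1.1 further enrolments.
- One week: 16.7 × 12/52 = 3.8 to 33.3 × 12/52 = 7.7.
- One month: 17 to 33.
- A full 3-month monitoring interval: 3 × 16.7 = 50 to 3 × 33.3 = 100. An event falling at random in that interval waits 1.5 months on average, which gives 25 to 50.

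The documents do not say which lag applies. These figures count enrolments, not harm.

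**Length of the all-cause window proposed below.** It runs from the first breath test to the 48-hour call. With both tests done, the shortest is 48 + 48 hours = 4 days and the longest is 30 days + 48 hours = 32 days (12.4, 12.5).

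**The case against.** The strongest reply is that the rule will almost never be tested. Section 5.2.3.2 reports no related events in 1466 + 74 = 1540 people given methacetin with this device. The one-sided 95% upper limit is 1 − 0.05^(1/1540) = 0.19%. At that rate 200 patients would yield 200 × 0.0019 = 0.39 events, and the chance of two or more, of any grade or type, is about 1 − e^(−0.39) × (1 + 0.39) = 6%. Two matching non-serious Grade 3 events would be far rarer. This stands as a limit on importance. It covers methacetin only, since 5.2.2.1 gives no denominator for octanoate, and it does not explain why a rule the protocol chose to have lacks a matching route.

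It can also be said that the sponsor will receive these events anyway. Data capture is electronic, 15.4 has the sponsor report all adverse events to authorities, and local regulations (9.2) or form instructions outside this document may set deadlines. That is fair, and a reader should not infer that the events go uncaptured or never reach the sponsor. Only a stated time limit is missing. Likewise, the list in 15.1 does not prove that the eCRF has no CTCAE field; it shows only that the protocol does not ask for one.

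A reader might infer from 15.5 that even a serious and unexpected listed event escapes the immediate call. The text does not establish this: 15.5 speaks of a form and 15.4 of a call. The reach of the exemption is unclear, no more. Nor do the documents support the idea that gut symptoms are the likely trigger, plausible as that is for an oral dose.

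Finally, the sponsor's outgoing alert is worded more widely than the incoming duty: "Exalenz Bioscience will notify all investigators of serious or unexpected adverse events when this information is of global importance to subject safety and welfare". Because it is limited to matters of global importance, this adds little.

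**Conclusion.** The mismatch is real and lies in the text: the criteria for prompt reporting do not cover all the events that the stopping rule counts. It is confined mainly to non-serious Grade 3 events, with an occasional non-serious Grade 4 event.

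It is tempting to conclude that 50 to 100 more patients would be enrolled before a trigger is noticed. That requires the sponsor to see nothing until a monitoring visit a full 3 months later. The practice for eCRF review is not stated, so the figure is only one end of an illustration that runs down to 4 to 8 patients at one week.

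The conclusion assumes that no document outside this file already sets a deadline for these events. With few events expected, it is a cheap improvement of minor priority. It says nothing against the 10.6 thresholds themselves.

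**What to change.** 1. In 15.4, require notice to the medical monitor within 24 hours of awareness for any CTCAE Grade 3 or higher event from the first breath test through the 48-hour call, whatever its cause. Require the same for any later Grade 3 or higher event with a reasonable possibility of causation by the device or drug. Use that test from 15.1, not the possibly-related category of 15.2, which rates only the device and presupposes a known response pattern that a first novel reaction would lack.
2. In 15.5, state that the exemption does not cover events reportable under item 1 or serious and unexpected events.
3. Record the CTCAE v4.0 grade in the adverse event section of the eCRF, beside the 15.3 severity.

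The cost is two added provisions, one data field and a few extra notifications. Some will be unrelated: 12.1 allows the biopsy up to a month after the first breath test, so a biopsy complication can fall inside the window of at most 32 days. The background rate of Grade 3 or higher events in that window is not given. Sites must already detect and grade such events to apply the 10.6 withdrawal rule, so the added work is the notice itself.

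One limit remains. The wording of 10.6 leaves open whether attribution to a breath test applies to the Grade 3 limb as well as to Grade 4. If the sponsor means Grade 3 events to count whatever their cause, the clause on later events must be widened to match.

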10.7 Early Withdrawal from the Study

Patients, their relatives, their representatives or the patients' physician may withdraw the patient from the study at any time if they feel the study is not in the patients' best interest, or they may be withdrawn by the investigator or sponsor for safety, behavioral, or administrative reasons. All withdrawals must be fully documented.

If the patient withdraws from the study and also withdraws consent for the disclosure of future information, no further evaluations should be performed and no additional data should be collected. Previously acquired data will be analyzed. This will not have any effect on the treatment that the patient receives.

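### The 10.6 study stop counts CTCAE Grade 3 events across patients, but section 15 records a different severity scale and sets no deadline for reporting a non-serious, test-related Grade 3 event

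*Combined protocol and SAP*

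**What the plan says.** Section 10.6 holds two rules, both on CTCAE v4.0.

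- Patient rule: a patient is withdrawn "if they have a CTCAE Grade 3 or higher regardless of whether the event is attributed to the drug", with an exception for accidents.
- Study rule: the study is discontinued if two or more patients given a substrate "develop the same CTCAE Grade 3 event or 1 patient develops a CTCAE Grade 4 or higher event due to one of the breath tests".

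Section 15 sets out how events are recorded and passed on.

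- The CRF entry listed in 15.1 is "The adverse event severity using the criteria outlined below". Those criteria are in 15.3. They have three levels and rest on symptoms; for example, "A mild adverse event is one that the symptoms are barely noticeable to the patient". Section 15 does not mention CTCAE and gives no mapping to its grades.
- 15.3 adds that "Serious and severe are not synonymous".
- 15.4 sets one prompt route from site to medical monitor: "Any serious and unexpected adverse event will be reported to the medical monitor immediately by telephone or fax". Other adverse events go into the case report form, with no time limit stated.
- 15.5 lists raised bilirubin, raised liver enzymes, nausea, vomiting and diarrhea, which "are excluded from expedited notification on an AE form, but should be reported in the follow-up section of the CRF form". It sets no grade limit.

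On withdrawal, 10.7 says "All withdrawals must be fully documented". Under 17.1, data go into an electronic CRF, and monitoring is estimated at a minimum of every 3 months or every 10 subjects per site. Section 11.7.8.2 tells the study to stop on a severe safety concern, but names no grade, count or responsible role.

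**The concern.** A stopping rule protects patients only if someone learns promptly that it has been met. The Grade 3 limb needs a count of matching events in different patients. Each site sees only its own patients, so the count has to be kept by someone who sees all sites, in the units of the rule. Section 15 supplies neither the units nor the timing, and no role is named to keep the count.

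Two matching, non-serious, test-related Grade 3 events at different sites could therefore meet the rule while other patients are still being given the substrates. Enrollment of 200 over 6 to 12 months (11.5, 10.8) means about 200/12 = 17 to 200/6 = 33 new patients a month if accrual is even. Each month of delay could expose about that many.

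**Working it through.** The plan gives no operating figure for the stop, so there is none to reproduce. The main check is textual.

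**Step 1: units.** The stop uses CTCAE grades, with a threshold of two patients at Grade 3 and one at Grade 4 or above. The recorded scale ends at severe. A severe entry cannot show which threshold applies. A symptom scale also fits laboratory changes poorly, although 15.1 counts clinically significant laboratory changes related to acetaminophen exposure as adverse events.

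**Step 2: timing.** The prompt route in 15.4 needs an event to be both serious and unexpected. Since 15.3 separates severe from serious, a non-serious Grade 3 event is possible, and 15.4 gives it no deadline. For the five findings in 15.5, expedited notice is removed at every grade.

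**Step 3: likelihood if the event must be related to a test.** Section 5.2.3.2 reports 1,466 chronic liver patients and 74 controls tested internally with methacetin, none with a related event: 1,466 + 74 = 1,540.

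- One-sided 95% upper bound: p = 1 − 0.05^(1/1540) = 0.00194, or 0.19%.
- Chance of two or more: 1 − (1−p)^N − N·p·(1−p)^(N−1).
- N=200: 1 − 0.678 − 0.264 = 0.058, or 5.8%.
- N=400 (the maximum in 11.5): 1 − 0.459 − 0.358 = 0.183, or 18.3%.

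These are ceilings at that bound, because they count any two related events. The rule needs two of the same type at Grade 3. Section 5.2.2.1 reports no octanoate complications but gives no denominator, so the bound covers methacetin only.

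**Step 4: a weaker source.** The same section cites 2,987 individuals in published methacetin work without reported adverse events. The same formula gives a bound of 0.10%, and 1.8% (N=200) or 6.2% (N=400). Published reports may omit events, so the internal figure is the safer one.

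**Step 5: likelihood if unrelated Grade 3 events counted.** The plan gives no background rate. The rates below are assumptions for one particular Grade 3 event.

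| Assumed rate per patient | N=200 | N=400 |
|---|---|---|
| 0.1% | 1.7% | 6.1% |
| 0.5% | 26.4% | 59.5% |
| 1% | 59.5% | 91.0% |

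The table shows why the attribution wording in 10.6 should be settled. It does not estimate the risk in this study.

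**The case against.** The strongest reply is that the events would be seen anyway.

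- Sites must already apply CTCAE v4.0 in order to withdraw a patient, and must document the withdrawal.
- Data sit in a central electronic system, and under 15.4 the sponsor reports all adverse events to authorities.
- 15.4 also has the sponsor notify all investigators of serious *or* unexpected events of global importance. Section 9.2 expects no test-related events, so a related Grade 3 event would probably count as unexpected even if not serious.
- An exclusion from expedited notice on an AE form (15.5) implies that other adverse events do receive such notice.
- The eCRF itself is not in the documents and may hold a CTCAE field.

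Much of this stands. A reader might infer that no prompt route exists at all, or that the CRF certainly lacks a grade. The documents do not show either. What they show is that 15.1 and 15.3 specify only the three-level scale, and that the route implied in 15.5 is not described in 15.4. None of these safeguards sets a deadline from site to sponsor or creates a cross-site count. The sponsor's notice to investigators also depends on the sponsor already knowing of the event.

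A reader might also infer that unrelated background events could stop the study, with the large probabilities in Step 5. That rests on assumed rates and on the less natural reading of 10.6. The patient rule disclaims attribution expressly. The study rule does not, and it ends with an attribution phrase.

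**Conclusion.** The mismatch is real, and it lies between rules the plan states. The stop is defined on CTCAE grades across patients, while section 15 specifies another scale and gives a non-serious, test-related Grade 3 event no deadline for reaching anyone who sees all sites.

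The gap is mainly in the Grade 3 limb. A serious and unexpected event, including one of Grade 4, reaches the medical monitor at once, and each affected patient is protected by withdrawal. It would go too far to conclude that test-related harm in general could pass unnoticed.

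The likelihood is low: at most 5.8% at N=200 and 18.3% at N=400 for two related events of any grade or type. This assumes that the attribution phrase covers both limbs and that the internal methacetin experience carries over to this study, including to octanoate. The length of any delay cannot be estimated, because data entry times, review times and the number of sites are not stated. The change is worth making because the rule exists to protect patients and the repair is cheap.

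**What to change.** 1. Specify a CTCAE v4.0 grade on the adverse event page of the CRF.
2. In 15.4, require immediate notice to the existing medical monitor, with the investigator's attribution and whether or not the event is serious, for (a) any CTCAE Grade 3 or higher event from the first substrate dose to the 48-hour call, and (b) any later one judged possibly related, probably related or related.
3. In 15.5, state that the exemption does not apply to these events. Later unrelated disease-progression events stay exempt, so long-term follow-up does not generate needless notices.
4. Name the medical monitor as keeper of the 10.6 count.
5. In 10.6, state that the attribution phrase applies to both limbs.

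No new committee is needed. The cost is wording in three sections, one CRF field, an amendment needing ethics committee or IRB approval (13.1), and a few extra notices. Apart from accidents, the first such event withdraws the patient, so there is about one notice per affected patient. If 1% to 5% of patients were affected (an assumption), that is 200 × 1% = 2 to 200 × 5% = 10 notices at N=200, and 4 to 20 at N=400.
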